**Study Procedures.**

1. **Study Visits.** There will be a total of three in-person study visits:

- Visit 1, week 0 (4-12 weeks of age)
- Visit 2, week 12 ± 10 days (~5 months of age)
- Visit 3, week 24 ± 10 days (~8 months of age)

Procedures during the study visits will take a total of approximately 3 hours and will usually be completed on the same day. If all procedures cannot be scheduled for the same day they will be scheduled for two days in a row. The study visits will include all of the following:

- Infant and maternal history collection including medications, therapies, infant feeding method, and adverse reactions (~30 minutes)
- Physical examination including length, weight, head circumference, arm span, waist circumference, stretched penile length, Tanner staging, and testicular size by Prader orchidometer (~30 minutes)
- Quantified body composition assessment by the PeaPod (~30 minutes)
- Standardized neurodevelopmental assessment (~30 minutes)
- Morning venous blood draw following a minimum of 180 minutes fasting (~30 minutes)
- Non-invasive urine and stool sample collection (~10 minutes)
- Visit 1 only: intramuscular injection and teach

	Visit 1: Week 0		Visit 2: Week 12		Visit 3: Week 24
Group A n=30		T T T		P P P	
Group B n=30		P P P		T T T	
Study Activity					
Medical History	X		X		X
Physical Exam	X		X		X
PeaPod	X		X		X
Developmental Eval	X		X		X
Blood draw	X		X		X
Urine/stool collect.	X		X		X
Safety Assessment	X	X X	X	X X	X

**Figure 6.** Overall study design, timeline and assessments. T=testosterone, P=placebo

2. **Injections/Intervention.** Participants in this study will receive a total of 6 injections. 25 mg testosterone cypionate (200 mg/mL) or placebo (saline) will be given via intramuscular injection every 4 weeks (study weeks 0, 4, 8, 12, 16, and 20). The total volume of each injection will be 0.125 mL. The first shot for all participants will be administered at CHCO before the end of study visit #1 and the infant will be observed for 15 minutes. Parents will elect to either have the 5 subsequent injections given by a nurse at CHCO or to give them at home themselves. If they elect to give them at home, a nurse in the Pediatric CTRC or in Endocrinology will teach the parents how to administer the shots. Parents will receive an automated email reminder 24 hours before the next injection is due. Parents will keep an administration log to document the injection was given.

Although our intent is to give all injections intramuscularly, if the parent inadvertently gives an injection subcutaneously it should not alter our validity. A recent study found subcutaneous testosterone injections are well tolerated and effective at raising serum testosterone levels, although pharmacodynamics may differ from intramuscular injections therefore this method will not be encouraged.

3. Interim surveys. A parent will complete a REDCap survey one week after each injection to capture pertinent information about the injection and potential side effects. One week out was chosen as most side effects attributable to the medication will be present by then and waiting longer may increase recall bias. This survey will serve as a drug administration log as well as interim safety monitoring. All survey results will be review by study staff and any potential unanticipated events or severe adverse events will be followed up with a phone call to the parent.

**Safety Considerations.** This testosterone dosing and duration is accepted practice for treatment of micropenis in this age group without reported side effects. We had no serious adverse events in our pilot study using this protocol. Intramuscular injections include the risk of inflammation and/or pain at the site of injection, sterile abscess, infection, and hypersensitivity reactions. Potential low-risk side effects of testosterone therapy include acne, pubarche, and increased erections. High doses and/or prolonged duration of androgen therapy in some populations has been associated with bone age advancement, venous thromboembolism, water retention, anaphalactoid reactions, suppression of clotting factors II, V, VII, and X, polycythemia, and priapism. Testosterone also suppresses spermatogenesis, however infants do not undergo spermatogenesis. The effect of early testosterone on later fertility is unknown.

*Likelihood of experiencing any risk:* moderate (temporary pain at injection site)

*Likelihood of experiencing serious risk:* very low

*Alternatives:* There are multiple formulations of testosterone, however all deliver much higher doses than proposed in this protocol. Injections are routinely administered as accepted standard of care in infants with micropenis, and are the choice of individuals currently advocating for testosterone in XXY infants. We have experience with testosterone gel in older populations, however even if we were able to deliver gel in an appropriate dose, risks of gel include unintentional contact, frequent application, skin reactions, and many of the possible side effects of testosterone therapy. Oxandrolone, an alternative androgen, is available as an oral formulation but has not been studied in this age group and appropriate dosing would be unknown. Therefore injections are the logical choice to study.

*Protection against risk:* Standard procedure for reducing infection risk will be utilized including sterile single use needles and skin preparation. Parents will be present and/or giving the injections. Infants will be observed for at least 15 minutes after their first injection to insure there are no immediate adverse reactions. Any subjects with a known allergy to any ingredients in the study drug or with a first-degree relative with a history of a blood clot will not participate in the study. Testosterone can be stored at room temperature, therefore no special precautions are required to ensure the safety of the medication.

*Monitoring for reactions:* One week after every testosterone injection, parents will be sent a brief REDCap survey via email to query for possible reactions. Parents will be given an optional log to record any side effects they notice at home to better help them complete the survey. At every study visit, a study team member will ask about all side effects, hospitalizations, surgeries, new diagnoses, and new medications. Parents will also be encouraged to report serious side effects to the study team immediately.

The PI will discuss any serious adverse events with Drs. [name] and [name] and all these events will be reported to regulatory bodies as required. A Data and Safety Monitoring Board (DSMB) will be comprised of a minimum of three clinicians/scientists with expertise in clinical trial conduct and methodology, XXY syndrome/development, and biostatistics. The DSMB will meet after every 20 subjects are enrolled. Members will review data on all adverse events, changes in growth parameters, and testicular function. There will not be any predetermined criteria for altering the study protocol or discontinuing the study, therefore these options will be at the discretion of the DSMB.

**Study Timeline.** The timeline for major study activities are in Table 1.

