### B. Description of Population to be Enrolled:

A total of 75 infants with XXY will be enrolled. We will include all races, ethnicities, and languages.

*Inclusion criteria:* Male infants with 47,XXY karyotype identified prenatally who are 4-12 weeks old (31 to 90 days of age). 47,XXY must be from a diagnostic test such as CVS, amniocentesis, or post-natal blood/tissue. Non-invasive prenatal screening results alone will not be accepted.

*Exclusion criteria:*

- 1) >20% mosaicism for a normal cell line
- 2) Gestational age at birth <36 weeks
- 3) Birth weight <2.5thile or >97.5thile for age (small or large for gestational age)
- 4) History of thrombosis in self or a first degree relative
- 5) Exposure to androgen therapy outside the study protocol
- 6) Use of medications known to affect body composition, such as growth hormone or insulin
- 7) Known allergy to the testosterone cypionate solution components including benyl benzoate, benzyl alcohol, or cottonseed oil

Involving children is imperative as boys <18 years of age with XXY are much a different population than adult men with XXY. Men with XXY have been shown to have a high prevalence of type 2 diabetes, metabolic syndrome, fatty liver disease, and psychosocial difficulties. Clearly these processes begin in childhood. The potential to intervene in a preventative fashion, prior to the onset of disease, is more promising and productive than trying to treat pre-existing disease. Infant boys are exposed to endogenous testosterone in the first few months of life known as the “mini-puberty period of infancy.” Animal and human studies suggest this is a critical period for biologic programming, and therefore cannot be replicated at any other point in life. Including children in this study design allows us to investigate testosterone as a targeted intervention at this critical time point with evaluation of early markers of disease and disability. The ultimate goal is to improve the lives of children and adults with this condition.

The age of the infants at enrollment was chosen 1) to allow assessment of testicular function during the expected mini-puberty period of infancy, 2) to assure visits 2 and 3 will be completed before the infant is 10kg, as this is the upper weight limit for the PeaPod (our body composition assessment tool), and 3) feedback from parents.

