**Consent.** When a child is identified through clinic or other method identified above, a member of the study team will contact the parent to inform them of the opportunity to participate in a study. In many cases, the parents will contact the PI, PRA or genetic counselor of the eXtraordinary Kids Clinic after hearing about the study from one of the above sources. Prior to any information being collected, verbal consent to ask questions pertaining to the inclusion/exclusion criteria will be obtained. A member of the study team will describe the study and will offer to email/mail the consent form to the parents so the parents have ample time to review prior to deciding whether to schedule the first visit and enroll in the study.

Prior to any research procedures being performed, a study team member will review the consent form in person in a private location. Both verbal and written consent will be required from a parent or legal guardian to enroll in the study. All of the subjects in this protocol are infants and therefore too young to assent/consent to research participation themselves. To minimize coercion, parents will not be paid for enrolling their child in the study and only reimbursement for reasonable travel will be provided. We will emphasize to parents their child's participation is entirely voluntary and can be withdrawn at any time. As part of the consent process, parents will be asked to summarize the study in their own words to ensure comprehension, and parents will have the opportunity to ask questions. If the consenting parent does not speak English, an interpreter will assist with the consent process and a short-form consent document in the parent's preferred language will be completed. If the consenting parent is blind, illiterate, or with reading limitations, the entire consent form will be read to the subject and witnessed by someone outside of the study team.

**Randomization.** Subjects will be randomized 1:1 using block randomization in groups of 20 to 1) receive T treatment in the first 12 weeks followed by placebo, or 2) placebo for the first 12 weeks followed by T. Investigational Drug Services at CHCO will generate the automated randomization list and dispense the study drug to maintain allocation concealment. All investigators and parents will remain blind to the intervention group.

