2. **NEURODEVELOPMENTAL ASSESSMENT:** The Alberta Infant Motor Scale (AIMS), Peabody Developmental Motor Scales -2 (PDMS-2), and the Bayley Scales of Infant Development – 3rd edition will be performed by a psychometrist trained to administer these standardized neurodevelopmental assessments. The **AIMS** is a performance-based and norm-referenced measure of infant gross motor maturation from birth to 18 months. It is intended to evaluate gross motor development over repeated assessments and has good reliability and predictive validity for later gross motor development. In a systematic review of neurodevelopmental tests, the AIMS had the best psychometric properties and clinical utility. The **PDMS-2** is a standardized assessment for infant development and includes six subtests to assess gross and fine motor scales from birth to 5 years. It is one

of the most common tools for discriminating normal from abnormal infant motor development. This instrument was chosen as a broad assessment of motor development with normative reference data, and strongly correlates with other motor assessments. The **Bayley 3** is a comprehensive standardized assessment for infant development containing three domains: Cognitive, Language, and Motor. The Bayley-3 is widely used to diagnosis developmental delays up to 3.5 years of age. Finally, a parent will complete the Adaptive Behavior Assessment System, 3rd edition (**ABAS 3**), a validated measure of adaptive skills across the lifespan, including infancy. The ABAS incorporates early developmental skills in areas such as feeding, sleep, play, self-regulation, and social development. The primary risk of the developmental evaluation is identification of developmental delays that may warrant further evaluation and/or intervention. This may cause psychological distress to the parent.

*Likelihood of experiencing any risk: low*

*Likelihood of experiencing serious risk: very low*

*Alternatives: None identified.*

*Protections against risk:* Parents will be made aware of the high prevalence of at least mild developmental delays in XXY. Parents will be present during the evaluation. If delays are identified, the study team will disclose this to the parent(s) in a private area with specific recommendations for next-steps, potentially including referrals and/or resources.

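### Parents are declared blind, but an oil-based testosterone solution is compared with saline, no masking of the dose is described, and parents may inject at home, which leaves the secondary parent-rated ABAS and parent-reported adverse events open to bias

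*Combined protocol and SAP*

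**What the plan says.** Section IV.C, Randomization, states without qualification: "All investigators and parents will remain blind to the intervention group". The only safeguard described there is that "Investigational Drug Services at CHCO will generate the automated randomization list and dispense the study drug to maintain allocation concealment".

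The products are given in Study Procedures, Injections/Intervention: "25 mg testosterone cypionate (200 mg/mL) or placebo (saline) will be given via intramuscular injection every 4 weeks". The vehicle of the active product appears in the exclusion criteria (section IV.B), which rule out infants with "Known allergy to the testosterone cypionate solution components including benyl benzoate, benzyl alcohol, or cottonseed oil". The one property stated to be common to all doses is volume: "The total volume of each injection will be 0.125 mL".

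The first dose is given at the hospital. After that, "Parents will elect to either have the 5 subsequent injections given by a nurse at CHCO or to give them at home themselves". Doses fall at weeks 0, 4, 8, 12, 16 and 20, and the arms exchange products from the week-12 dose.

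Parents also supply outcome data. Under Neurodevelopmental Assessment (section IV.D), "a parent will complete the Adaptive Behavior Assessment System". Under Interim surveys, a parent fills in a REDCap form on side effects a week after a dose. Table 2 lists ABAS and the number of adverse events as Aim 2 secondary outcomes at weeks 12 and 24, with adverse events taken from parents' reports.

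**The concern.** Pharmacy control of the randomization list protects assignment. It does not by itself keep the arm hidden from someone who later draws up, sees or injects the dose. An oil solution and saline would be expected to differ in appearance and flow, and the plan describes no matched vehicle, no opaque or pre-filled syringe, and no check of whether parents guessed the arm.

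The person best placed to notice is the person who rates the ABAS and reports side effects. Expectation is not neutral: section III says the parents consulted in informal focus groups and surveys saw large benefit and little risk in testosterone. If some parents work out the arm, a difference in ABAS or in reported events could reflect belief rather than drug. Adaptive functioning and safety are both named in the Aim 2 hypotheses, and section IV.G says the results will inform clinical management.

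**Working it through.** **1. What a home-injecting parent handles.** Each infant gets three doses of one product (weeks 0, 4, 8) and three of the other (weeks 12, 16, 20). The week-0 dose is given at the hospital.

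- Before the week-12 visit, the parent handles two doses (weeks 4 and 8) of a single product, with nothing to compare it with.
- From the week-12 dose, the parent can handle the second product and compare. The week-24 reports are therefore the most exposed.
- Choosing a nurse does not fully remove exposure: the risk-protection paragraph has parents present for injections they do not give.

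**2. Which outcomes depend on the parent.**

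| Outcome | Source | Exposure |
|---|---|---|
| %BF z-score (Aim 1 primary) | PeaPod, blinded assessor | Largely protected |
| AIMS (Aim 2 primary) | Trained psychometrist | Largely protected |
| ABAS (secondary) | Parent | Exposed |
| Adverse events (secondary) | Parent report | Exposed |

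**3. Check of the plan's figures.** The plan gives no figure for blinding. The figures used here agree with the text:

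- Volume: 25 mg ÷ 200 mg/mL = 0.125 mL.
- Sample size: for a difference of 0.5 with 0.65 read as an SD, two-sided alpha 0.05 and 27 per group, power is 80.7% by the normal approximation and 79.2% by the t-test, against the stated 80%.

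**4. Illustration for ABAS.** The Data Analysis Plan analyses developmental scores as in Aim 1, that is, with a two-sided t-test at 0.05. Assume no true effect. Let knowledge of the arm shift the rating by *b* SD in a share *g* of families, so the arm-average shift is *d* = *b* × *g*. Both *b* and *g* are assumptions; the documents give neither. The test statistic then follows a noncentral t with 2 × 27 − 2 = 52 degrees of freedom and noncentrality *d* × √(27/2) = 3.674 × *d*. The false-positive rate is the chance that it exceeds the two-sided 5% limit.

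Example: *b* = 0.2, *g* = 1 gives noncentrality 0.735 and a rate of 11.1%.

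| Shift *b* | A quarter affected | Half affected | All affected |
|---|---|---|---|
| 0.2 SD | *d* = 0.05: 5.4% | *d* = 0.10: 6.5% | *d* = 0.20: 11.1% |
| 0.3 SD | *d* = 0.075: 5.8% | *d* = 0.15: 8.4% | *d* = 0.30: 19.1% |
| 0.4 SD | *d* = 0.10: 6.5% | *d* = 0.20: 11.1% | *d* = 0.40: 30.3% |

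If all 75 infants are enrolled and 10% drop out, about 34 per arm remain (75 × 0.9 ÷ 2 = 33.75). The all-affected rates are then 12.8%, 23.0% and 36.9%. The calculation takes a shift at one visit and does not separate week 12 from week 24.

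**5. A conflict on the survey.** Interim surveys sends the form after every dose, whichever product was given. Monitoring for reactions ties it to testosterone doses. Read literally, the second would reveal the arm by whether a survey arrives.

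**The case against.** The documents do not say how either product looks or handles, or how doses leave the pharmacy. Masking may be set out in a pharmacy procedure that was not supplied. That stands. A reader might infer that parents will certainly know the arm, or that the trial is not blind. The text supports only that blinding is claimed for products with different vehicles and that no masking is described.

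A reader might also take 11% to 30% as the expected error rate. That range needs every family to be affected. Home injection is elective and its uptake is not given. With a quarter to a half of families affected, the range is about 5% to 11%.

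Further limits also stand:

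- Adverse events are only described, not tested, so the false-positive figures do not apply to them.
- The examiner-administered AIMS is already the lead neurodevelopmental outcome. Section IV.D does not repeat that the psychometrist is blinded, but nothing there has the psychometrist handle doses.
- Section IV.E already says the weeks 12 to 24 results are secondary and rest on assumptions.
- Feeding method and physical therapy are recorded, with adjustment if the groups differ. Outside androgen exposure is an exclusion, and new medications are asked about at each visit. The documents do not support calling co-interventions unaddressed.
- The remark on perceived benefit explains a recruitment difficulty. It is not a result of the separate survey of 34 parents, so it does not show that all surveyed parents held that view.

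Finally, acne, pubic hair or more frequent erections could unblind a parent whatever the syringe looks like. This limits what masking can achieve, but it strengthens the case for asking parents what they guessed and why.

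**Conclusion.** The concern holds in a limited form. As written, the plan claims parental blinding, describes nothing that would maintain it after dispensing, and takes two sets of secondary outcomes from the people most likely to notice a difference. The exposure is greatest at week 24.

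For ABAS the illustrative false-positive rate runs from about 5% to 30% at 27 per arm. It depends on an assumed rating shift and an assumed share of families affected, and the point does not rest on any one value. It does rest on the inference that oil and saline can be distinguished.

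A reader might infer that the body-fat or AIMS result is compromised. The documents do not support that, because neither is rated by a parent. The point should be corrected, but it does not threaten either efficacy primary. Treatment guesses have to be collected while the trial runs, so that part cannot be left to the analysis.

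**What to change.** 1. Have Investigational Drug Services dispense both products in masked (opaque or over-wrapped) pre-filled syringes of the same volume and needle, and say so in the protocol. This is subject to a pharmacy check of storage for doses supplied ahead for home use, since no study visit falls between weeks 0 and 12.
2. Add one treatment-guess question, with the reason for the guess, to the existing REDCap survey after the week-8 and week-20 doses, and report it by arm. The reason helps to separate syringe cues from visible drug effects.
3. State that ABAS and parent-reported events will be interpreted as possibly unblinded, and that ABAS alone will not support a neurodevelopmental claim.
4. Reconcile Interim surveys with Monitoring for reactions so that receiving a survey does not reveal the arm.

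The cost is a little pharmacy work, one survey question and a few sentences. Products, dose, schedule, sample size and primary analyses stay as they are. The limit is that resistance on injection and visible androgen effects remain, so masking is improved but not guaranteed.

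### The only required post-injection observation follows injection 1, which is saline in the placebo-first arm, so that arm's first testosterone dose (injection 4) has no required observation and may be given at home

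*Combined protocol and SAP*

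**What the plan says.** Section IV.C (Randomization) assigns half the infants to "placebo for the first 12 weeks followed by T". Under Study Procedures, Injections/Intervention, the placebo is saline and the six injections fall at weeks 0, 4, 8, 12, 16 and 20. On the first of these the protocol says: "The first shot for all participants will be administered at CHCO before the end of study visit #1", with 15 minutes of observation. On the rest: "Parents will elect to either have the 5 subsequent injections given by a nurse at CHCO or to give them at home themselves".

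The list of visit procedures includes the injection only as "Visit 1 only: intramuscular injection and teach". The later visits are "Visit 2, week 12 ± 10 days" and "Visit 3, week 24 ± 10 days".

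Under Safety Considerations, Protection against risk, the purpose of the observation is given: "Infants will be observed for at least 15 minutes after their first injection to insure there are no immediate adverse reactions". The same paragraph keeps out "Any subjects with a known allergy to any ingredients in the study drug", and the exclusion criteria in section IV.B name the vehicle components concerned (benzyl benzoate, benzyl alcohol, cottonseed oil).

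**The concern.** The observation rule follows the injection number, not the product. In the testosterone-first arm the two coincide. In the placebo-first arm the observed injection is saline, which contains neither the hormone nor the vehicle components named in the exclusion criteria. Three tolerated saline injections say nothing about hypersensitivity to the active solution. When that arm switches to testosterone at week 12, the dose may be given by a parent at home, and nothing requires observation at CHCO either.

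At stake is a safeguard against immediate reactions in young infants that, as written, covers the first testosterone dose in only one of the two arms. The observation gap itself does not bias the comparison over weeks 0 to 12.

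**Working it through.** The plan gives no figure to reproduce. The check sets the injection schedule against the observation rule, then counts infants and intervals.

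**Schedule** (Study Procedures and Figure 6, in days)

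| Injection | Day | Testosterone-first | Placebo-first | Observation required |
|---|---|---|---|---|
| 1 | 0 | testosterone | saline | yes, 15 min at CHCO |
| 2, 3 | 28, 56 | testosterone | saline | no |
| 4 | 84 | saline | **testosterone (first)** | **no** |
| 5, 6 | 112, 140 | saline | testosterone | no |

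The protocol does not plan to observe later doses in either arm, so only the first active dose is counted.

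**Infants affected**
- Figure 6: 30 in the placebo-first arm.
- Section IV.B enrols 75, randomized 1:1 in blocks of 20. Three full blocks give 3 × 10 = 30 per arm. The remaining 15 infants add 5 to 10, so the arm has 35 to 40.
- Section IV.F allows 10% drop-out but not its timing. If all of it came before week 12: 0.9 × 30 = 27, or 0.9 × 35 to 0.9 × 40 = 31.5 to 36.
- Uptake of home injection is not given, so the number first dosed at home ranges from 0 to all of these.

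**What the pilot can exclude.** Section III reports 18 infants, no serious adverse events, and only increased appetite and acne as side effects. With zero immediate reactions, the one-sided 95% upper bound is 1 − 0.05^(1/n). If all 18 had been treated, which they were not, this is 15.3%. If half were treated (an assumption, since the number is not stated), n = 9 gives 28.3%. These bounds show how little 18 infants can rule out. They do not estimate a reaction rate.

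**Effect on intervals of moving injection 4 to Visit 2**
- Visit 2 falls on days 74 to 94 and Visit 3 on days 158 to 178.
- Injection 6 to Visit 3 now: 158 − 140 = 18 to 178 − 140 = 38 days.
- With injection 4 at Visit 2, injection 6 falls on days 130 to 150. If Visit 3 keeps only its present window, the gap becomes 158 − 150 = 8 to 178 − 130 = 48 days.
- If Visit 3 is targeted 84 days after Visit 2, the gap at target is 28 days. Allowing ±10 days inside days 158 to 178: Visit 2 on day 74 gives a gap of 28 to 38 days; day 84 gives 18 to 38; day 94 gives 18 to 28. Overall it is 18 to 38, as now.
- Injection 3 to injection 4: 74 − 56 = 18 to 94 − 56 = 38 days, instead of 28. One of these two doses is always saline, so no interval between two testosterone doses changes.
- Testosterone-first arm, last testosterone dose to Visit 3: 158 − 56 = 102 to 178 − 56 = 122 days, before and after the change.

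**Order at week 12.** Injection 4 is due on day 84 and Visit 2 may be as late as day 94. Figure 6 draws the injection after the visit, but the text does not fix the order. A placebo-first infant could therefore receive testosterone up to 94 − 84 = 10 days before the primary measurement.

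**The case against.** The strongest reply is that the protocol does not contradict itself. Its observation rule refers to the first injection and never mentions first exposure to testosterone. Hypersensitivity is listed among the risks of intramuscular injections in general, and observing injection 1 addresses that in both arms. Anaphylactoid reactions are mentioned only for high-dose or prolonged androgen therapy in some populations. The regimen is described as established for micropenis at this age without reported side effects. Known allergy is an exclusion, a parent is present at or gives each injection, parents are urged to report serious effects at once, and a survey follows a week later, with a phone call for any event of concern. Some families will choose a CHCO nurse for injection 4 anyway.

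Much of this stands. That observation should cover the first testosterone dose is an inference, drawn from the allergy exclusions and the listed reactions. The accurate description is that no staff observation is required, not that every such dose would go unwatched. The mitigations keep the point minor, but none replaces clinic observation: the exclusion catches only known allergy, the survey comes a week later, and the rest depends on the parent.

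It is also fair to say that the change involves more than one extra injection at a visit. Those costs are set out with the fix.

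**Conclusion.** The gap is real and minor. As written, the first testosterone dose is observed by rule in the testosterone-first arm only. In the placebo-first arm, one first active dose per infant reaching week 12 has no required observation: 30 infants by Figure 6, or 35 to 40 of 75, before drop-out; 27, or about 32 to 36, if all the 10% drop-out comes first. The number dosed at home cannot be determined from the documents.

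The schedule facts come directly from the text. The judgement that the safeguard should extend to first testosterone exposure is inferred. This is a cheap safety improvement, not an error in the analysis. Fixing the order of injection 4 and the week-12 assessments also protects the primary measurement, which is a further reason to make the change.

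**What to change.** **Change**
- Give injection 4 to every infant in both arms at CHCO at the end of Visit 2, after the week-12 assessments and blood draw, with at least 15 minutes of observation. Treating both arms alike keeps the blind.
- In the visit procedure list, add the injection to Visit 2; teaching can stay at Visit 1. Limit the home option to injections 2, 3, 5 and 6.
- Under Protection against risk, require observation after the first injection of each treatment period.
- Time injections 5 and 6 at 4 and 8 weeks after the actual injection 4.
- Target Visit 3 at 84 days after Visit 2, within 10 days of that target and inside its existing week-24 window.

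**Cost**
- Protocol wording, one injection and about 15 more minutes at a visit every family already attends. The automated reminders need re-timing, and the IND file would probably need updating.
- Families lose the home option for one dose.
- The gap between injections 3 and 4 varies from 18 to 38 days.
- If Visit 2 falls at the edge of its window, the usable Visit 3 window shrinks from 20 days to 10, which matters for families who travel.

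A lighter alternative is to observe only families who choose CHCO for injection 4 and to teach the others the signs of a reaction. That leaves first doses given at home without staff observation.
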